3.5. Determination of Sample Size

The primary endpoint is the difference between EN3835 and placebo in the mean change from Baseline (Day 1) to Day 57 on the foot pain subscale (total score on 9 items) of the FFI ranging from 0 (“None”) to 4 (“Extreme”).

Assuming a difference in the mean change from Baseline to Day 57 in the pain subscale of FFI between EN3835 and placebo of 5.0 with a 10 standard deviation and 85% statistical power

using a 2-sided test ($\alpha = 0.05$), 73 participants per treatment group (146 in total) will be needed to detect this difference between the 2 treatment groups. Assuming a dropout rate of 15%, the total sample size will be 172, 86 per treatment group for the study.

Participants will be screened to ensure that approximately 172 participants are randomized into 2 treatment groups, an EN3835 group and a placebo group in a 1:1 ratio.

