6.3.1. Handling of Missing Data for the Primary Endpoint

The foot pain subscale score will be recorded at baseline and at each visit (ie, Day 15, 29, 43, and 57).

The primary endpoint will be the change from baseline at Day 57. This value will be missing if the participants have missing data due to discontinuation from the study prior to Day 57 or due to a missed assessment or lost to follow up.

The missing data at Day 57 will be imputed for the participants who withdraw from the study prior to Day 57 using multiple imputation washout model (Section 7.6.1.2) to explore the possibility of data missing not at random (MNAR). In the multiple imputation washout framework, for participants who withdraw from the study early, their missing values will be

imputed under the assumption that their outcome would be similar to those in the placebo group with similar background characteristics. Multiple imputation methods will be used to account for uncertainty in the imputation process and results from the imputed datasets will be combined using Rubin's method.(4)

In addition, to assess the impact of missing values, sensitivity analyses using Mixed Model Repeated Measure (MMRM) (Section 7.6.1.3) without imputation and with imputation using Tipping Point Analyses (Section 7.6.1.2) will be performed on primary endpoint and key secondary endpoints. If the primary analyses of primary endpoint and key secondary endpoints result is not significant ($p\text{-value} > 0.05$), no sensitivity analyses (tipping point) will be performed.

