- **Method of Analyses:** The change from Baseline (Day 1) to Day 57 in the total foot pain subscale score will be calculated after the missing data imputation has been performed and will be analyzed using an Analysis of Covariance (ANCOVA) model on each multiply imputed dataset. The model will include the fixed effect of treatment group and FFI pain subscale score at baseline, the maximum of Nodule length/Nodule width, and the total number of nodules as covariates. Treatment effects from these ANCOVA analyses will then be combined using Rubin's Method via the SAS PROC MIANALYZE procedure. The LSM estimate for each treatment, the LSM of treatment difference, their corresponding 95% confidence interval (CI) and associated p-value will be provided (Section 7.6.1.2 for more details on this analyses).
- **Sensitivity analyses to primary endpoint:** The following sensitivity analyses will be performed on primary efficacy endpoint to assess the impact of missing data:
 - A sensitivity analyses will be performed based on all observed data up to Day 57. The change from Baseline (Day 1) to Day 57 will be analyzed using an MMRM (Section 7.6.1.3).
 - Another sensitivity analyses will be performed using MMRM with imputation of missing values for participant who discontinue treatment or who are withdrawn from the study. The imputed missing values will be adjusted using a TPA (Section 7.6.2).
- **Supportive analyses to primary endpoint:** The primary efficacy endpoint will also be analyzed using ANCOVA by FAS and mITT population.

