 - Early withdrawal from the study is the potential intercurrent event that could occur. If participants do not have nodular hardness at Day 57 due to early withdrawal, the missing values will be imputed before the analyses using a multiple imputation washout model. In multiple imputation washout model, all participants who are randomized and have a baseline assessment will be considered (Section 7.6.1.2 for details on imputation).
- **Population Level-Summary measure:** Least square mean (LSM) estimate for treatment difference between EN3835 and placebo.
- **Method of Analyses:** The change from baseline (Day 1) to Day 57 in nodular hardness will be calculated after the missing data imputation has been performed and will be analyzed using ANCOVA model on each imputed dataset. The model will

include the fixed effect of treatment group and average nodular hardness at baseline, the maximum of Nodule length/Nodule width, and the total number of nodules as covariates. Treatment effects from these ANCOVA analyses will then be combined using Rubin's Method via the SAS PROC MIANALYZE procedure. The LSM estimate for each treatment, the LSM of treatment difference, their corresponding 95% confidence interval (CI) and associated p-value will be provided (Section 7.6.1.2 for more details on this analyses).

- **Sensitivity analyses to secondary endpoint:** Following sensitivity analyses will be performed on secondary efficacy endpoint to assess the impact of missing data:
 - A sensitivity analyses will be performed based all observed data up to Day 57. The change from baseline (Day 1) to Day 57 will be analyzed using a MMRM (Section 7.6.1.3).
 - Another sensitivity analyses will be performed using MMRM with imputation of missing values for participant who discontinue treatment or who are withdrawn from the study. The imputed missing values will be adjusted using a TPA (Section 7.6.2).
- **Supportive analyses to secondary endpoint:** The secondary efficacy endpoint will also be analyzed using ANCOVA by FAS and mITT population..

The descriptive statistics for observed and change from baseline at each visit of the hardness measurements (as measured by durometer) by treatment group will be provided for participant level and nodule level.

A listing of nodular hardness by participant will be provided.

7.6.3.3.2. Nodule Level Analyses:

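### At the plan's 15% dropout, the washout primary analysis pooled by Rubin's rules has about 75% power, not the stated 85%, because Rubin's standard error is conservative under placebo-based imputation and the SAP does not say so

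*SAP*

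**What the plan says.** - **Imputation.** SAP 6.3.1 uses a washout model for participants who withdraw before Day 57. It presents this as a way to explore data missing not at random. Missing values are "imputed under the assumption that their outcome would be similar to those in the placebo group with similar background characteristics".
- **Variance.** SAP 7.6.1.1 fits an ANCOVA to each imputed dataset. "Treatment effects from these ANCOVA analyses will then be combined using Rubin's Method via the SAS PROC MIANALYZE procedure". The primary 95% CI and p-value come from that step. SAP 7.6.3.1 (key secondary endpoint 1) and SAP 7.6.3.3.1 (key secondary endpoint 3) use the same method: "Treatment effects from these ANCOVA analyses will then be combined using Rubin's Method". The readable text names no other variance estimator for these analyses.
- **Model.** "The model will include the fixed effect of treatment group and FFI pain subscale score at baseline"; maximum nodule dimension and number of nodules are the other covariates.
- **Sample size (SAP 3.5, matching Protocol 10.1).** The assumed difference is "between EN3835 and placebo of 5.0 with a 10 standard deviation and 85% statistical power", and "using a 2-sided test ($\alpha = 0.05$), 73 participants per treatment group (146 in total) will be needed". Then: "Assuming a dropout rate of 15%, the total sample size will be 172, 86 per treatment group for the study". Allocation is 1:1.
- **Redaction.** The imputation steps in SAP 7.6.1.2 are blacked out, so the readable text does not settle whether EN3835 dropouts' own earlier visits enter the model.
- **Conflict.** SAP 7.6.2 describes the analysis in 7.6.1.2 as resting on a missing-at-random assumption, which is not how 6.3.1 describes it.

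**The concern.** The sample size rests on a plain comparison of 73 completers per arm. The primary analysis is different in two respects. Washout imputation pulls the estimate toward zero, because dropouts contribute no treatment effect. Rubin's rules then attach a standard error that does not shrink along with the estimate.

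The reason is a mismatch between two models. The imputation model gives EN3835 dropouts the placebo mean, so their imputed mean moves with the placebo mean and cancels from the difference. The ANCOVA does not know about that restriction, and Rubin's within-plus-between variance gives no credit for it.

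What is at stake is power and the width of the intervals for the primary endpoint and key secondary endpoints 1 and 3. The primary test is the entry to the hierarchy (SAP 6.5), and SAP 6.3.1 drops the tipping-point analysis when the primary result is not significant. Amendment 04 had already lowered the power target from 90% to 85%.

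**Working it through.** **Inputs.** Difference 5.0, SD 10, two-sided 0.05, 85% power, 15% dropout and 86 per arm (SAP 3.5); placebo-like imputation (SAP 6.3.1); Rubin's rules (SAP 7.6.1.1). Assumptions added here: dropout completely at random with fraction d in each arm, imputation from baseline only, no variance explained by covariates, and the 5.0-point effect applying to participants with Day 57 data.

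**The plan's own figure.** A two-sample t-test with 73 per arm has 85.1% power (84.6% with 72), and 146/0.85 = 171.8, rounded up to 172. Both stated numbers reproduce.

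**Closed form, n per arm, many imputations.**

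- Estimate: (1−d) × completer difference. At d = 0.15 this is 0.85 × 5.0 = 4.25.
- Repeated-sampling variance: (1−d)² × 2SD²/[n(1−d)] = 2SD²(1−d)/n.
- Rubin within-imputation variance: 2SD²/n. Between-imputation variance: the placebo parameter draw is common to both arms and cancels, leaving the residual draws, d² × 2SD²/(dn) = 2dSD²/n. Total: 2SD²(1+d)/n. Under an effect δ, add δ²d(1−d)/n, because imputed EN3835 values spread the arm.
- SE ratio under the null: √[(1+d)/(1−d)].

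**At d = 0.15.**

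- Repeated-sampling SE: √(200 × 0.85/86) = 1.406.
- Rubin SE, null: √(200 × 1.15/86) = 1.635, ratio 1.163.
- Rubin SE, δ = 5: √(2.674 + 0.037) = 1.647, ratio 1.171.
- Size: 2Φ(−1.96 × 1.163) = 2.3%.
- Power with Rubin: Φ[(4.25 − 1.96 × 1.647)/1.406] = Φ(0.727) = 76.6%.
- Power with the matching SE: Φ(4.25/1.406 − 1.96) = Φ(1.063) = 85.6%.

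**Over a range of dropout.**

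| d | Estimate | Repeated-sampling SE | Rubin SE (null) | Ratio | Size | Power, Rubin | Power, matching SE | Loss (points) |
|---|---|---|---|---|---|---|---|---|
| 5% | 4.75 | 1.486 | 1.563 | 1.05 | 3.9% | 87.1% | 89.2% | 2 |
| 10% | 4.50 | 1.447 | 1.599 | 1.11 | 3.0% | 82.4% | 87.5% | 5 |
| 15% | 4.25 | 1.406 | 1.635 | 1.16 | 2.3% | 76.6% | 85.6% | 9 |
| 20% | 4.00 | 1.364 | 1.671 | 1.22 | 1.6% | 69.6% | 83.5% | 14 |

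**Simulation of the full procedure** (Bayesian regression imputation from placebo, ANCOVA with the three SAP covariates, Rubin's rules, 50 imputations, 16,000 trials) at 15%: SE ratio 1.17, size 2.3%, power 75.3% against 84.3%. A separate simulation with 30 imputations and 2,500 trials gave size 2.5% and power 74% against 84%. At 10% dropout it gave 80% against 86%.

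**Sensitivity at 15%.**

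- EN3835 dropouts also conditioned on their earlier visits (assumed between-visit correlation 0.4 to 0.8): ratio 1.09 to 1.14, size 2.7 to 3.3%, power about 77 to 82%, loss 5 to 8 points.
- Placebo dropouts imputed from earlier visits, EN3835 dropouts from baseline only: ratio 1.16 to 1.18, size 2.1 to 2.2%, loss about 9 points.
- Unequal dropout: 15% in EN3835 and 5% in placebo gives 77.1% against 86.2%. Reversed, it gives 84.5% against 86.9%. Dropout in the EN3835 arm drives the loss.

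**The case against.** **Rubin's variance is a defensible choice.** A reader might infer that the standard error is simply wrong and should be replaced in the primary test. The numbers do not support that. With nobody missing, the SE would be √(200/86) = 1.525. With 73 completers per arm it is √(200/73) = 1.655. Rubin gives 1.635, close to the completer value, so imputation adds no information. The repeated-sampling SE of 1.406 is about 8% below the no-dropout value and falls further as dropout rises. Paired with an estimate that shrinks by the same factor, it returns in essence the completer test statistic: 0.85 × difference divided by 0.85 × completer SE. The primary p-value would then carry almost no penalty for missing data. Reasonable statisticians differ on this, so the objection stands against changing the primary test.

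**No stated error rate is breached.** A reader might also infer a type I error problem, because this test opens the hierarchy. There is none. Protocol 10.4 promises an overall rate below 0.05, and a size of 2.3-2.5% meets it.

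**The size depends on unseen steps and on a planning assumption.** This is true. SAP 7.6.1.2 is redacted, 15% may not be reached, and participants who stop treatment are encouraged to stay (Protocol 8.1). The result must be stated as a range. If 7.6.1.2 were an ordinary within-arm missing-at-random imputation, as SAP 7.6.2 implies, the point would fall away. SAP 6.3.1 and the washout label would then be wrong.

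What the objections leave standing is that the stated power describes a different analysis from the planned one.

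**Conclusion.** The concern holds as a mismatch between the stated and actual operating characteristics, in the conservative direction. At 15% dropout in both arms, with baseline-only imputation and no covariate gain, Rubin's SE exceeds the repeated-sampling SE by about 16%. The nominal 5% test runs at about 2.3-2.5%, the 95% CI covers about 97.5%, and power is about 75% rather than 85%. About 9-10 points of that gap come from the SE.

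The loss from the SE is about 2 points at 5% dropout, 5-7 at 10% and 14 at 20%. It is about 5-8 at 15% if EN3835 dropouts' earlier visits enter the redacted steps. Covariate adjustment would raise the absolute power: in a simulation with an assumed baseline-outcome correlation of 0.3, it was 78.7% against 86.4%.

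The sample size arithmetic is correct on its own inputs; it does not describe the planned analysis. All of this takes SAP 6.3.1, not SAP 7.6.2, as the description of SAP 7.6.1.2.

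**What to change.** Keep the washout estimate and Rubin's rules for the primary test, and make four changes before unblinding.

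1. **SAP 3.5 and Protocol 10.1:** restate the power for the planned washout, ANCOVA and Rubin analysis over 5-20% dropout. On the plan's inputs this is about 87% at 5%, 80-82% at 10%, 75% at 15% and 70% at 20%. The sponsor should rerun it with the actual imputation steps.
2. **SAP 7.6.1.1, 7.6.3.1 and 7.6.3.3.1:** say that Rubin's variance is deliberately conservative under placebo-based imputation, and give approximate size and coverage as a range. Under the closed form, size is 3.9% to 1.6% and coverage 96.1% to 98.4% as dropout goes from 5% to 20%.
3. **Same sections:** prespecify a supportive SE, CI and p-value from a bootstrap that resamples participants within arm, re-imputes and refits each time.
4. **SAP 6.3.1 and 7.6.2:** reconcile the two descriptions of 7.6.1.2 (missing not at random and placebo-like, or missing at random).

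The cost is a less favourable stated power, revised wording and a little extra programming. The estimand, point estimate and primary test do not change.

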7.6.1.2. Multiple Imputation Method

Multiple imputation will be used to account for uncertainty in the imputation process and results from the imputed datasets will be combined using Rubin's method. ANCOVA will be used as the analyses method. The main steps of the implementation of the washout imputation are described below.

[REDACTED]

In addition, the observed and change from Baseline in individual item score, subscale score (%), and Total Pain Subscale Score on Day 15, 29, 43, and EOS (Day 57) will be summarized descriptively by treatment group.

The change from Baseline in the Total Foot Pain Subscale Score in the ANCOVA derived LSM at Day 57, will be presented using a bar graph with error bars depicting the SE (on the y-axis) and treatment group along the x-axis by ITT, FAS and mITT population.

The mean change from Baseline in the Total Foot Pain Subscale Score with observed data by treatment group will be presented using a line graph with error bars depicting the SE (on the y-axis) and visit along the x-axis by ITT, FAS and mITT population.

A listing of FFI individual item scores, subscale score (%), composite score (%), total subscale score, and total score by participant will be provided.

7.6.1.3. Sensitivity Analyses using MMRM (Observed Data)

Sensitivity analyses will be performed on observed data using MMRM. The mean change in Total Pain Subscale Score from Baseline to Day 57 in EN3835 compared to placebo will be analyzed using a MMRM. An unstructured covariance matrix will be used to model the covariance of within-participant values. The Kenward-Roger approximation will be used to estimate denominator degrees of freedom. If the convergent criteria are not met then other covariance matrix structure, ie., autoregressive (1) (AR (1)) will be used for model. The MMRM model will include:

[REDACTED]

The least square mean (LSM) estimate for each treatment at EOS, the LSM of treatment difference, their corresponding 95% confidence interval (CI) and associated p-value will be provided.

7.6.2. Sensitivity Analyses using MMRM using Tipping Point Analyses (TPA)

The analyses in Section 7.6.1.2 is based on the MAR assumption, to evaluate the impact of deviations from the MAR assumption, a delta adjustment multiple imputation method will be used here to find the tipping point where the result is no longer statistically significant.

There are 3 different steps which will be followed for sensitivity analyses. The following steps will be performed to impute the missing data using the methods described in Section 6.3.1:

[REDACTED]

[REDACTED]

All steps above are repeated with different values of the shift parameter until the tipping point is reached or all possible values are explored. The tipping point can be identified when the result is no longer statistically significant (one p-value >0.025). It is possible a tipping point is not reached if little to no data is missing.

Once tipping point is reached, if implausible departure from MAR is needed to change the results from statistically significant to insignificance, the results of the primary endpoint are considered to be robust. If the tipping point obtained for overturning the primary endpoint result is clinically plausible, the conclusion can be questioned and viewed with caution.

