6.5. Multiplicity Adjustment

Multiplicity arising from testing of secondary endpoints will be addressed by using a fixed sequence hierarchical testing procedure. A step-down testing procedure will be applied where inference for an endpoint in the predefined hierarchy is dependent on statistical significance having been achieved for the previous endpoints in the hierarchy.

The hierarchy of endpoints is defined as follows:

- Primary endpoint
- Key secondary endpoint 1
- Key secondary endpoint 2
- Key secondary endpoint 3

All the tests will be performed at the 0.05 level of significance following the pre-specified order. The testing of the first key secondary endpoint will be conducted if the result of the primary

endpoint is statistically significant and testing of the second key secondary endpoint will be conducted if the result of the first key secondary endpoint is statistically significant and so on.

The other secondary endpoints and exploratory endpoints do not fall under this hierarchical approach as no multiplicity adjustment will be made for such endpoints and only nominal p-values will be reported.

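### The tipping-point section calls the washout primary analysis MAR, so the meaning of delta = 0 is contradictory and robustness is judged against the wrong assumption

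*SAP*

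**What the plan says.** **Primary imputation.** SAP 6.3.1 imputes missing Day 57 pain scores "using multiple imputation washout model (Section 7.6.1.2) to explore the possibility of data missing not at random (MNAR"). Participants who withdraw are imputed on the assumption that their "outcome would be similar to those in the placebo group with similar background characteristics". Section 7.6.1.2 describes itself as the washout imputation.

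**Primary model.** SAP 7.6.1.1: the change from baseline "will be analyzed using an Analysis of Covariance (ANCOVA) model on each multiply imputed dataset", with results combined by Rubin's method.

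**Tipping-point analysis.** SAP 7.6.2 makes four statements that matter here:
- On the primary analysis: "The analyses in Section 7.6.1.2 is based on the MAR assumption, to evaluate the impact of deviations from the MAR assumption".
- On its own imputation: "The following steps will be performed to impute the missing data using the methods described in Section 6.3.1".
- On the rule: the primary result counts as robust "if implausible departure from MAR is needed to change the results from statistically significant to insignificance".
- On the cut: the tip is where the result is "no longer statistically significant (one p-value >0.025"). SAP 7.6.3.2.2 repeats this cut for the clinician global impression of change.

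The section title, 7.6.1.1 and Table 27 all place the tipping-point analysis in an MMRM.

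**Test level.** SAP 6.5: "All the tests will be performed at the 0.05 level of significance following the pre-specified order". The sample-size sections of both documents specify a two-sided test at 0.05.

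**Cross-reference.** SAP 6.3.1 sends the reader to 7.6.1.2 for the tipping-point analysis, but it stands in 7.6.2.

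**The concern.** The same section of the SAP cannot be both washout (MNAR) and MAR. The label matters because the decision rule is built on it. A tipping-point analysis is read as a distance: how far the imputed values must move from a starting assumption before significance is lost. Here the starting assumption has two definitions. If it is MAR, delta = 0 is not the primary analysis. If it is washout, the shifts are not departures from MAR.

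This is the only delta-based check on the primary endpoint and on the two continuous key secondary endpoints (SAP 7.6.3.1 and 7.6.3.3 both refer to 7.6.2). The protocol leaves its details to the SAP. If the reference point is still open at unblinding, the same data can be described as comfortably robust or as needing caution.

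**Working it through.** **1. The plan's own figure.** Inputs (Protocol 10.1, SAP 3.5): difference 5.0, SD 10, two-sided alpha 0.05, power 85%, dropout 15%.
- Normal approximation: 2 × (1.960 + 1.036)² × 10² / 5² = 71.8, so 72 per arm.
- Two-sample t-test: 73 per arm (power 0.851).
- 73 / 0.85 = 85.9, so 86 per arm and 172 in total. The stated figures reproduce.

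**2. Set-up for the tipping shift.** Let E be the effect among completers, d the fraction missing in each arm, and zc the critical value. Take SE = 10 × √(2 / (86 × (1 − d))). A shift of delta points in the unfavourable direction, applied to the imputed EN3835 values only, lowers the estimate by d × delta.
- Counted from MAR (imputed EN3835 values carry the full effect): delta = (E − zc × SE) / d.
- Counted from washout (imputed EN3835 values look like placebo, so the estimate starts at E × (1 − d)): delta = (E × (1 − d) − zc × SE) / d.
- The two differ by E exactly, whatever SE, d or zc may be.

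**3. Design values, d = 15%, zc = 1.960.** SE = 10 × √(2 / 73.1) = 1.654, and 1.960 × 1.654 = 3.242.
- From MAR: (5.0 − 3.242) / 0.15 = 11.7 points.
- From washout: (4.25 − 3.242) / 0.15 = 6.7 points.

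**4. Range over assumed inputs.**

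| Missing per arm | Effect | Tip from MAR | Tip from washout |
|---|---|---|---|
| 5% | 5.0 | 38.7 | 33.7 |
| 10% | 5.0 | 18.5 | 13.5 |
| 15% | 5.0 | 11.7 | 6.7 |
| 20% | 5.0 | 8.3 | 3.3 |
| 15% | 4.0 | 5.1 | 1.1 |

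With effect 4.0 and 15% missing, a tip about 5 points from MAR is only about 1 point beyond what the primary analysis already assumes.

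**5. The 0.025 cut.** One-sided 0.025 gives z = 1.960, identical to two-sided 0.05. Two-sided 0.025 gives z = 2.241, and at the design values with 15% missing the tip comes earlier: 8.6 from MAR and 3.6 from washout. At effect 4.0 and 15% missing, the washout estimate is 3.4 and z = 3.4 / 1.654 = 2.06. That passes 1.960 but fails 2.241, so a significant primary result would count as tipped with no shift at all.

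**6. ANCOVA versus MMRM.** This was compared by simulation on complete data: 86 per arm, unstructured covariance, assumed correlations 0.5 to 0.7, 60 runs. Mean estimate −4.98 by both methods; SE 1.323 (ANCOVA) and 1.320 (MMRM); mean absolute difference 0.04 points, largest 0.37.

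**The case against.** The strongest reply is that the visible text leans towards a washout start. Section 7.6.2 says it imputes by the 6.3.1 methods, and 6.3.1 describes washout. On that reading the reported shift would be the smaller, correct one, and only the MAR wording is wrong. The detailed steps in 7.6.1.2 and 7.6.2 are redacted, so neither start can be confirmed. This stands: the overstatement in the working is conditional on counting from MAR. It does not remove the contradiction, because the rule for calling the result robust is still written in terms of MAR.

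The rest of the reply limits how far the point can be taken. A reader might infer three stronger things, none of which the documents support:
- *That the analysis cannot measure the robustness of the primary result.* A MAR-anchored delta is still informative if the washout position is marked on its scale, and the caution half of the rule in 7.6.2 asks about clinical plausibility without naming MAR.
- *That 0.025 is the wrong level.* The SAP does not state its sidedness. Read as one-sided, it matches the two-sided 0.05 test. If it were two-sided it would be stricter and would understate robustness.
- *That moving from ANCOVA to MMRM changes the answer.* On complete data the difference is negligible.

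The analysis is also conditional: under 6.3.1 the tipping-point step is not run when the primary p-value exceeds 0.05. An observed-data MMRM is planned alongside it.

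**Conclusion.** The contradiction is real and rests on unredacted text: 6.3.1 and 7.6.1.2 against 7.6.2, and 7.6.2 against itself. The reference point for delta is not coherently defined, and the robustness rule names an assumption the primary analysis does not make.

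If delta is counted from MAR, the margin is overstated by about the treatment effect, 5 points at the design values. If it is counted from washout, the number is right and the criterion is wrong. The tipping figures assume equal missingness in both arms, an active-only shift, washout that removes the whole effect in dropouts, and a simplified SE. An SE of 1.67 instead of 1.654 gives 11.5 and 6.5; the 5-point gap does not change.

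The undefined sidedness of 0.025 is a smaller gap that needs one phrase. The model mismatch is a matter of tidiness. None of this touches the primary estimate, its p-value, the testing order or the type I error. Severity is moderate: it affects how a conditional sensitivity analysis is read.

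**What to change.** Amend the SAP before database lock, the point by which the protocol requires it to be final:
1. In 7.6.2, replace the MAR statement with one that the primary analysis uses washout imputation (MNAR, placebo-like). In 6.3.1, point the tipping-point cross-reference to 7.6.2.
2. Apply the delta increments to the washout-imputed datasets and analyse each with the primary ANCOVA and Rubin's rules, so that delta = 0 reproduces the primary result.
3. Judge plausibility as points worse than placebo-like, not as departure from MAR.
4. In 7.6.2 and 7.6.3.2.2, state the cut as two-sided p > 0.05 (equivalently one-sided p > 0.025).
5. If a MAR-anchored version is wanted, keep it as an extra, with the washout position marked on its delta scale.

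The cost is SAP wording and modest reprogramming. No new data are needed.
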